2.2 STUDY OBJECTIVES

Primary objectives

1. To explore baseline characteristics and drug utilization patterns in patients with nonvalvular atrial fibrillation (NVAF) who newly initiated NOACs, warfarin, or used aspirin
 - Demographic and clinical characteristics: Age, sex, types of health insurance, CHA₂DS₂-VASc score, HAS-BLED score, Charlson Comorbidity Index score, etc.
 - Descriptions of index treatment: Types of medication received, index dose intensity
 - Drug utilization pattern: Each patient will be followed-up until the first treatment modification occurs, or study ends (November 30, 2016).
2. To compare effectiveness including hemorrhagic stroke, ischemic stroke and systemic embolism of antithrombotic therapies in patients with NVAF with the following antithrombotic therapies: NOACs, warfarin, and aspirin
 - Primary effectiveness outcome: Composite of hemorrhagic stroke, ischemic stroke, and systemic embolism
 - Secondary effectiveness outcomes: Individual outcome of hemorrhagic stroke, ischemic stroke, and systemic embolism
3. To compare safety of anti-thrombotic therapies in patients with NVAF with the following antithrombotic therapies: NOACs, warfarin, and aspirin
 - Primary safety outcome: Major bleeding including gastrointestinal bleeding or intracranial bleeding and other bleeding
 - Secondary safety outcomes: Individual outcome of major bleeding

[NOTE] comparative analyses will be performed contingent on a feasibility assessment based on the descriptive analyses.

Secondary objectives

1. To explore and understand more detailed drug utilization patterns
 - Standard dose versus reduced dose

- Pattern of usage (i.e., switching, discontinuation) and clinical events preceding the pattern
- Compliance (i.e., medication possession ratio)

2. To compare effectiveness and safety of antithrombotic therapies versus not using therapies among low risk patients (low score of CHA₂DS₂-VASc)

3 ANALYSIS SETS/ POPULATIONS

3.1 FULL ANALYSIS SET

Inclusion criteria

Patients must meet all of the following inclusion criteria to be eligible for inclusion in the study:

1. Patients aged 18 years or older on the index date
2. Patients had ≥ 1 medical claim for AF (refer to Table 1) before or on the index date with at least one hospitalization or at least two outpatient visits:

[Diagnosis codes for inclusion criteria]

KCD-6 ¹⁾	KCD-7 ²⁾
I48 (Atrial fibrillation and flutter)	I48 (Atrial fibrillation and flutter)
I480 (Atrial fibrillation)	I480 (Paroxysmal atrial fibrillation)
I481 (Atrial flutter)	I481 (Persistent atrial fibrillation)
	I482 (Chronic atrial fibrillation)
	I483 (Typical atrial flutter)
	I484 (Atypical atrial flutter)
	I489 (Atrial fibrillation and atrial flutter, unspecified)

KCD-6, Korean version of ICD-10 (6th revision); KCD-7, Korean version of ICD-10 (7th revision)

1) KCD-6 diagnosis codes will be used from 1 July 2015 to 31 December 2015.

2) KCD-7 diagnosis codes will be used from 1 January 2016 to 30 November 2016.

[NOTE] KCD code is based on ICD-10 and almost similar, but KCD code is slightly different from ICD-10 (e.g., ICD-10 is more subdivided and extensive than KCD code).

3. Patients prescribed aspirin, warfarin, or NOACs in intake period (from July 1, 2015 to November 30, 2016)
[Note] NOACs include apixaban, dabigatran and rivaroxaban.

Exclusion criteria

Patients meeting any of the following criteria will not be included in the study.

1. Medical claims indicating diagnosis or procedure for hip/knee replacement surgery within 6 weeks prior to index date
2. Medical claims indicating a diagnosis code indicative of rheumatic mitral valvular heart disease, mitral valve stenosis during the 12-month baseline period
(Valvular AF / Prosthetic heart valves)
3. Medical claims indicating a diagnosis code of VTE (Venous thromboembolism) during the 12-month baseline period
4. Medical claims indicating a diagnosis or procedure code of transient AF, or cardiac surgery during the 12-month baseline period
(Thyrotoxicosis, Hypertrophic cardiomyopathy, elective defibrillation, radiofrequency ablation, or left atrial appendage occlusion)
5. Medical claims indicating a diagnosis code of others during the 12-month baseline period
 - (End-stage chronic kidney disease / Kidney transplant / Dialysis / Pericarditis)
6. For the comparison of “NOAC versus NOAC”, and “NOAC versus warfarin”, patients with any OACs (apixaban, dabigatran, rivaroxaban, or warfarin) in the pre-index period (from 1 year prior to the day before index date)
 - *[NOTE] Patients prescribed antiplatelets in the pre-index period will not be excluded.*
7. For the comparison of “NOAC versus aspirin”, patients with following medications in the pre-index period (from 1 year prior to the day before index date)
 - NOAC user: OACs (apixaban, dabigatran, rivaroxaban, warfarin)
 - Aspirin user: none
 - *[NOTE] NOAC user is defined as OAC naïve user and aspirin user is allowed to have OACs or antiplatelets in the pre-index period.*

Cohorts

To avoid increasing type I error when multiple comparisons occur, this full analysis set will be splitted into multiple sub-analysis sets as follows:

1. NOAC vs NOAC (both as OAC naïve users)
 - A. Sub-dataset 1: patients with index treatment of apixaban and patients with index treatment of dabigatran
 - B. Sub-dataset 2: patients with index treatment of apixaban and patients with index treatment of rivaroxaban
 - C. Sub-dataset 3: patients with index treatment of dabigatran and patients with index treatment of rivaroxaban

[NOTE] The index date will be defined as date of the first prescription of NOAC in patients with NVAF. To identify new users, a look-back observation period from 1 year prior to the day before the index date will be used and must indicate no OAC use during this period. The diagnosis date of NVAF could occur from January 1, 2007 up to and including the index date.

2. NOAC vs warfarin (both as OAC naïve users)
 - A. Sub-dataset 4: patients with index treatment of apixaban and patients with index treatment of warfarin
 - B. Sub-dataset 5: patients with index treatment of dabigatran and patients with index treatment of warfarin
 - C. Sub-dataset 6: patients with index treatment of rivaroxaban and patients with index treatment of warfarin

[NOTE] The index date will be defined as date of the first prescription of NOAC or warfarin in patients with NVAF. To identify new users, a look-back observation period from 1 year prior to the day before the index date will be used and must indicate no OAC use during this period. The diagnosis date of NVAF could occur from January 1, 2007 up to and including the index date.

3. NOAC (OAC naïve user) vs aspirin (no restrictions of antiplatelet or OAC use in the pre-index period)
 - A. Sub-dataset 7: patients with index treatment of apixaban and patients with index treatment of aspirin
 - B. Sub-dataset 8: patients with index treatment of dabigatran and patients with index treatment of aspirin
 - C. Sub-dataset 9: patients with index treatment of rivaroxaban and patients with index treatment of aspirin

[NOTE] The index date will be defined as date of the first prescription of NOAC or aspirin in patients with NVAF during the intake period (from July 1, 2015 to November 30, 2016). To identify NOAC users, a look-back observation period from 1 year prior to the day before the index date will be used and must indicate no OAC use during this period. However, OAC use or antiplatelet use during a look-back observation period from 1 year prior to the day before the index date will be allowed for aspirin users. The diagnosis date of NVAF could occur from January 1, 2007 up to and including the index date.

Each patient was followed until discontinuation or switching of index treatment, outcome occurrence, or study ends (November 30, 2016).

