**Data analysis:** Patients will be matched on demographic and clinical characteristics. All outcome variables will be summarized descriptively through the tabular and graphical display of mean values, medians, ranges, and standard deviations of continuous variables of interest and frequency distributions for categorical variables. Effectiveness and safety outcomes of treatments will be estimated from time-to-event models. The 95% confidence intervals for the estimates will be calculated and  $p < 0.05$  will be considered significant. All analyses will be carried out using SAS version 9.4. Analysis and reporting will be compliant with Strengthening the Reporting of Observational Studies in Epidemiology (STROBE) recommendations.

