## 8.7 Data analysis

- All outcome variables will be summarized descriptively through the tabular and graphical display of mean values, medians, ranges, and standard deviations of continuous variables of interest and frequency distributions for categorical variables.
- Patients with aspirin, warfarin, and NOACs will be matched via propensity-score method. Patients will be matched on patient demographics (i.e., age, sex) and clinical (i.e., CHA2DS2-VAsC score, Charlson Comorbidity Index score, etc) variables. Other propensity score method (i.e., covariate adjustment, inverse probability of treatment weighting (IPTW)) will also be used. A Cox proportional hazards model, to account for differences in follow-up time and right data censoring, will be used to compare effectiveness and safety outcomes between treatment groups.
- Comparative analyses will be performed contingent on a feasibility assessment based on the descriptive analyses
- All analyses will be carried out using SAS version 9.4. The 95% confidence intervals for the estimates will be calculated and p < 0.05 considered significant.
- Sensitivity analysis of performing IPTW using the propensity score derived from multinomial model will be conducted.

Detailed methodology for summary and statistical analyses of data collected in this study will be documented in a Statistical Analysis Plan (SAP), which will be dated, filed and maintained by the sponsor. The SAP may modify the plans outlined in the protocol; any major modifications of primary endpoint definitions or their analyses would be reflected in a protocol amendment.

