5 STATISTICAL METHODOLOGY AND STATISTICAL ANALYSES

5.1 STATISTICAL METHODS

Descriptive Analysis:

- All outcome variables will be summarized descriptively through the tabular and graphical display of mean values, medians, ranges, and standard deviations for continuous variables of interest and frequency distributions for categorical variables.
- The proportion of antithrombotics (aspirin, clopidogrel, aspirin and clopidogrel combination, warfarin, NOACs) at index date will be examined.
- Appropriate tests (e.g., t-test, chi-square test) will be used based on the distribution of the measure. The $p < 0.05$ considered significant.

Multivariate Analysis:

Propensity score method

The estimation of propensity score will be performed to control for confounders in each sub-dataset: (1) each NOAC versus NOAC; (2) each NOAC versus warfarin; (3) each NOAC versus aspirin.

Propensity scores are estimated by logistic regression analyses that incorporate potential treatment predictors as independent variables and types of index treatment as dependent variable (e.g., apixaban=1, warfarin=0). Covariates in the logistic regression model will

include variables such as age, sex, CCI score, CHA₂DS₂-VASc score, HAS-BLED score, and comorbidities, but the final list of these covariates will be discussed and determined after reviewing the results of descriptive analysis of the pre-matched datasets. Further, we will report the *c*-statistic of the propensity score that indicates the degree to which the propensity score model discriminates between treated patients and untreated patients.

After estimation of propensity score, we will perform propensity score matching (PSM). 1:1 matching without replacement will be performed.

The populations would be first matched using PSM according to their index treatment. For these matched populations we should then explore the proposed subgroups by: making an assessment of patient numbers in the subgroups and checking that patient characteristics are still similar between the index treatments in the subgroups. If they are similar, then conduct interaction term analysis is being conducted to determine whether the treatment effect varies between the subgroups. If the populations are no longer similar in characteristics, then re-matching via PSM will be performed for the subgroups.

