Covariate adjustment using propensity score will also be performed. This approach has an advantage of using the whole observations whereas matching approach uses part of observations which were successfully matched.

Inverse probability of treatment weighted (IPTW)

We will perform an inverse probability of treatment weighted (IPTW) analysis. Every person will be weighted by the inverse of the probability of receiving the treatment actually received (i.e., PS in the treated and (1-PS) in the untreated).

Balance diagnostics

We will compare and assess the balance of baseline variables (e.g., continuous variable, dichotomous variable, interaction terms, or squares of continuous variable) between treated and control subjects in the weighted sample using standardized difference (Austin et al., 2015).

IPTW diagnostics

The distribution of weights will be carefully checked because some patients, those treated contrary to prediction, may receive very large weights (11, 12). To address the presence of extreme weights, we will consider several approaches, including use of stabilized weights, or trimmed or truncated weights (11-13). The stabilized weights will be implemented based on the following equation (11):

IPTW stabilized = $E*PE/PS + (1-E)*(1-PE)/(1-PS)$

- E: treatment (E=1), no treatment (E=0).
- PE: overall marginal prevalence of the treatment exposure.
- PS: estimated propensity score.

Balances between treatment groups will be evaluated by the standardized differences of all covariates, using a threshold of 0.1 to determine an imbalance.

Cox proportional hazards model

Cox proportional hazards model will be used to compare event rates between the treatment groups, with warfarin or antiplatelets as the primary reference in each sub-dataset: (1) each NOAC versus NOAC; (2) each NOAC versus warfarin; (3) each NOAC versus aspirin.

Cox model stratification (dummy variable method and true stratification method) will be performed to examine whether the stratum-to-stratum differences exist. To check the proportional hazards assumption, we will employ both the graphical methods (i.e., log-log plot, observed-expected plot, Schoenfeld residual plot) and statistical tests using the time-dependent covariate. If the assumption does not meet, we will employ either a stratified model or an interaction term between time and variable of interest (i.e., treatment indicator).

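### SAP 3.1 claims that splitting the cohort into nine pairwise sub-datasets prevents type I error inflation; it does not, and no comparative result is labelled as not adjusted for multiplicity

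*SAP*

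**What the plan says.** SAP 3.1, under Cohorts, introduces the split of the full analysis set with its reason: "To avoid increasing type I error when multiple comparisons occur, this full analysis set will be splitted into multiple sub-analysis sets as follows". Nine sub-datasets follow: three NOAC versus NOAC, three NOAC versus warfarin, and three NOAC versus aspirin. SAP 5.1 gives each its own propensity score model and Cox model. SAP 2.2 names one primary effectiveness outcome (the stroke/systemic embolism composite) and one primary safety outcome (major bleeding).

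On the threshold, Protocol 8.7 says: "The 95% confidence intervals for the estimates will be calculated and p < 0.05 considered significant". The Protocol abstract says the same. The SAP's only significance sentence sits under Descriptive Analysis in 5.1. For the Cox models the SAP promises a hazard ratio and a 95% CI, but its example Table 6 also has a P value column with no note.

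On method, SAP 5.1 plans matching ("1:1 matching without replacement will be performed"), then "Covariate adjustment using propensity score will also be performed", then "We will perform an inverse probability of treatment weighted (IPTW) analysis".

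**The concern.** The sentence in SAP 3.1 is the only place where either document addresses multiplicity, and it presents the issue as solved. A report could cite it as the study's multiplicity method. A reader would then take each p < 0.05, or each 95% CI that excludes 1, as protected against the number of comparisons made. What is at stake is how those p-values and intervals may be read. The estimates themselves are not affected.

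The NOAC–NOAC contrasts deserve most care. The SAP introduction says there are no head-to-head trials of these drugs, so readers are likely to look to these results.

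**Working it through.** The plan states no family-wise error rate, so there is no figure to reproduce. The check is whether the split could supply the claimed protection, and how large the rate is without it.

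**Inputs from the documents**
- Comparisons: 3 + 3 + 3 = 9 (SAP 3.1).
- Level per test: 0.05 (Protocol 8.7 and abstract). Two-sided is assumed, to match the 95% CI.
- Overlap: each NOAC is in four sub-datasets (apixaban 1, 2, 4, 7; dabigatran 1, 3, 5, 8; rivaroxaban 2, 3, 6, 9). Warfarin and aspirin are in three each.
- No arm sizes, event rates or outcome correlation are given.

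**Step 1: does splitting help?** Suppose the nine sub-datasets shared no patients. The tests would be independent, and the chance of at least one false positive would be

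1 − 0.95^9 = 0.370.

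A complete split therefore gives 37.0%, not 5%. Shared arms make the tests correlated and pull the rate below 37.0%. That reduction comes from the overlap, not from the splitting.

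**Step 2: allow for the overlap.** Nine z-tests among five arms were simulated with no true differences, each two-sided at 0.05 (1,000,000 replicates). For two contrasts that share arm i:
- full cohort: correlation of size (1/n_i) / √[(1/n_i + 1/n_j)(1/n_i + 1/n_k)];
- 1:1 matched, with the matched patients of arm i taken as a random subset: √(m_ij·m_ik) / (2·n_i), where m_ij = min(n_i, n_j).

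With equal arms both formulas give 1/2. The assumed information ratios, in the order apixaban : dabigatran : rivaroxaban : warfarin : aspirin, and the results for one primary outcome are:

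| Assumed ratios | Full cohort | 1:1, whole smaller arm matched |
|---|---|---|
| equal | 0.271 | 0.271 |
| 2:2:3:5:10 | 0.253 | 0.303 |
| 0.1:0.3:1:3:10 | 0.214 | 0.321 |

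If only 50–80% of the smaller arm finds a match, contrasts share fewer patients and the rate rises to about 0.30–0.36.

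**Step 3: a narrower null.** The SAP introduction reports noninferior or superior results for NOACs against warfarin in trials, so no difference anywhere is a worst case. With only the three NOAC–NOAC contrasts null:
- one outcome: 0.116–0.122 (full cohort), 0.122–0.134 (complete matching); independent limit 1 − 0.95^3 = 0.143;
- both primary outcomes, with correlation 0 to 0.8 between them: 0.176–0.229 (full cohort), 0.184–0.250 (complete matching); independent limit 1 − 0.95^6 = 0.265.

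**Step 4: is control supplied elsewhere?** Neither document contains an adjusted level, an ordering of tests, a p-value correction, or a statement that comparative results are not adjusted for multiplicity. The feasibility condition in SAP 2.2 may reduce the number of comparisons, but it does not address the error rate of those that remain.

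**The case against.** The best defence is that an observational study with separate pairwise questions need not adjust at all, and that each comparison keeps its own 5% error rate. Both parts are true. But each comparison would keep its 5% without the split, and the SAP sentence speaks of multiple comparisons, where the rate does rise. The fault is the claim of protection, not the lack of adjustment.

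Three stronger readings are tempting, and the documents do not support them.

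- *The p < 0.05 rule is itself an error, so the Protocol must drop it or the plan must adjust.* An unadjusted threshold is a choice on which reasonable statisticians differ. The Protocol makes no claim about family-wise error.
- *The true rate is 60% or more.* Nine comparisons by two outcomes give 18 tests, and 1 − 0.95^18 = 0.603. That needs independence, but arms are shared, and the hemorrhagic stroke codes count in both primary outcomes. Simulated values across both outcomes are 31–54% under the assumptions above. Effectiveness and safety are also separate objectives, so the per-outcome figures are the main ones. The 18 is a maximum, subject to feasibility.
- *Three propensity score methods triple the tests.* No method is called primary, but SAP 5.1 says matching comes first, and Protocol 8.7 and SAP 5.2 introduce covariate adjustment and IPTW as other methods also to be used. The multinomial IPTW is expressly a sensitivity analysis. No error rate was computed over methods, and the figures here take one method per comparison.

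One limit on precision also stands. The simulation uses fixed, disjoint arms. In SAP 3.1 the index date depends on the comparison (first NOAC; NOAC or warfarin; NOAC or aspirin within the intake period). A patient who starts on aspirin and later moves to a NOAC could thus be in the aspirin arm of one sub-dataset and a NOAC arm of another. The third decimal means nothing, but this does not rescue the SAP sentence.

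**Conclusion.** The concern holds. SAP 3.1 states an error-control property that the design does not have, and nothing else in either document supplies it or warns the reader.

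If no drugs differed, the chance of at least one false positive over nine tests of one primary outcome is about 21–27% with full-cohort contrasts, 27–32% with complete 1:1 matching, 30–36% with partial matching, and 37.0% if independent. For the NOAC–NOAC tests alone it is about 12–13% per outcome and 18–25% across both, with full-cohort contrasts or complete matching.

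These sizes are illustrative. They rest on assumed arm sizes, fixed disjoint arms, and an outcome correlation of 0 to 0.8. The conclusion does not rest on them: no setting tried comes near 5%, and the narrowest is still more than twice nominal. A reader might infer that the hazard ratios or intervals are wrong; they are not.

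**What to change.** 1. **SAP 3.1:** delete the type I error rationale. Say instead that the sub-datasets define the population, index date, propensity score model and Cox model for each pairwise comparison, which is what SAP 3.1 and 5.1 already use them for.
2. **SAP 5.1 and a footnote to Table 6:** state that the comparative p-values and 95% CIs are not adjusted for multiplicity. The words 'for multiplicity' are needed. In a propensity score study a bare 'unadjusted' would be read as crude, and these hazard ratios are adjusted for confounding.

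Optional, at the sponsor's choice:
- Put matching wording in Protocol 8.7 and the abstract at the next amendment. Protocol 9.3 requires prospective ethics approval of amendments, so this need not hold up the SAP correction.
- If formal control is wanted, name one primary analysis method, fix the number m of comparisons that pass feasibility before any outcome is compared, and apply Holm within each primary outcome. The first step is 0.05/m; with m = 9 that is 0.05/9 = 0.0056. The 95% CIs would still need the multiplicity label.

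The required change is two SAP wording edits and one footnote. It needs no new data and changes no hazard ratio or interval. The price is weaker claims of significance.

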### 8.2.2 Exclusion criteria

Patients meeting any of the following criteria will not be included in the study.

1. Medical claims indicating diagnosis or procedure for hip/knee replacement surgery within 6 weeks prior to index date
2. Medical claims indicating a diagnosis code indicative of rheumatic mitral valvular heart disease, mitral valve stenosis during the 12-month baseline period  
(Valvular AF / Prosthetic heart valves)
3. Medical claims indicating a diagnosis code of VTE (Venous thromboembolism) during the 12-month baseline period
4. Medical claims indicating a diagnosis or procedure code of transient AF, or cardiac surgery during the 12-month baseline period

(Thyrotoxicosis, Hypertrophic cardiomyopathy, Elective defibrillation, radiofrequency ablation, or left atrial appendage occlusion)

5. Medical claims indicating a diagnosis code of other conditions during the 12-month baseline period  
(End-stage chronic kidney disease / Kidney transplant / Dialysis / Pericarditis)
6. For the comparison of “NOAC versus NOAC”, and “NOAC versus warfarin”, patients with any OACs (apixaban, dabigatran, rivaroxaban, or warfarin) in the pre-index period (from 1 year prior to the day before index date)
  - *[NOTE] Patients prescribed antiplatelets in the pre-index period will not be excluded.*
7. For the comparison of “NOAC versus aspirin”, patients with following medications in the pre-index period (from 1 year prior to the day before index date)
  - NOAC user: OACs (apixaban, dabigatran, rivaroxaban, warfarin)
  - Aspirin user: none
  - *[NOTE] NOAC user is defined as OAC naïve user and aspirin user is allowed to have OACs or antiplatelets in the pre-index period.*

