2.1 STUDY DESIGN

This study will use a retrospective cohort design in which the treatment effectiveness and safety outcomes of new use of NOACs compared to other NOACs, new use of warfarin, and aspirin will be estimated in patients with atrial fibrillation using the Korean Health Insurance Review & Assessment Service (HIRA) database. Comparative analyses will be performed contingent on a feasibility assessment based on the descriptive analyses. Propensity score method and Cox proportional hazards models will be used to account for selection bias, differences in follow-up time, and right data censoring. This will allow us to minimize selection bias and confounding bias and provide outcome data amenable to rapid clinical interpretation (i.e., time-to-event analysis, hazard ratios). Furthermore, HIRA database will allow us to preserve the population-based longitudinal data collection advantages. The overall study design is described in Figure 1.

[figure not shown]

Figure 1. Study design scheme

Study population

Subjects with atrial fibrillation (between January 1, 2007 up to and including the index date*) who newly initiated NOACs, warfarin, or used aspirin between July 1, 2015 and November 30, 2016 in the Korean Health Insurance Review & Assessment Service (HIRA) database.

*Index date is the first prescription date of study drugs, including NOACs, warfarin, and aspirin.

Data source

South Korea has a universal health coverage system that the National Health Insurance covers approximately 97% of the overall South Korean population. The claims data of Health Insurance Review & Assessment Service (HIRA) contains 46 million patients per year that account for 90% of the total population in Korea and include claims from almost 80,000 healthcare service providers across South Korea as of 2011.

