Diabetes with chronic complication	E10.2-E10.5, E10.7, E11.2-E11.5, E11.7, E12.2-E12.5, E12.7, E13.2-E13.5, E13.7, E14.2-E14.5, E14.7	2
Hemiplegia or paraplegia	G04.1, G11.4, G80.1, G80.2, G81.x, G82.x, G83.0-G83.4, G83.9	2
Any malignancy, including leukemia and lymphoma	C00.x-C26.x, C30.x-C34.x, C37.x-C41.x, C43.x, C45.x-C58.x, C60.x-C76.x, C81.x-C85.x, C88.x, C90.x-C97.x,	2
Renal disease	I12.0, I13.1, N03.2-N03.7, N05.2-N05.7, N18.x, N19.x, N25.0, Z49.0-Z49.2, Z94.0, Z99.2	2
Moderate or severe liver disease	I85.0, I85.9, I86.4, I98.2, K70.4, K71.1, K72.1, K72.9, K76.5, K76.6, K76.7	3
AIDS/HIV	B20.x-B22.x, B24.x	6
Metastatic solid tumor	C77.x-C80.x	6

Table 12. Baseline Medications

Class	Drug
NSAIDs	Bromfenac, Celecoxib, Diclofenac, Etodolac, Fenoprofen, Flurbiprofen, Ibuprofen, Indomethacin, Ketoprofen, Ketorolac, Naproxen, Meclofenamate, Mefenamic acid, Meloxicam, Nabumetone, Oxaprozin, Piroxicam, Sulindac, Tolmetin
Antiplatelets	Aspirin, Clopidogrel, Prasugrel, Ticlopidine, Cilostazol, Abciximab, Tirofiban, Dipyridamole, Ticagrelor
PPI	Omeprazole, Pantoprazole, Lansoprazole, Rabeprazole, Esomeprazole, Dexlansoprazole
H ₂ -receptor antagonists	Cimetidine, Ranitidine, Famotidine, Nizatidine, Roxatidine, Lafutidine
Antiarrhythmics	Quinidine, Procainamide, Mexiletine, Propafenone, Flecainide, Amiodarone, Bretylium, Dronedarone, Propranolol, Atenolol, Esmolol, Verapamil, Diltiazem, Sotalol
Digoxin	Digoxin
Statins	Atorvastatin, Fluvastatin, Lovastatin, Pitavastatin, Pravastatin, Roxuvastatin, Simvastatin

Table 13. Exclusion Criteria

Condition	KCD Code or Korean Procedure Codes
Valvular AF/ prosthetic heart valves	I05, I08, I09, I34, Q23, T820, T826, Z952, Z953, Z954 - Korean Procedure Codes: M6580, M6581, M6582, O1791, O1792, O1793, O1794, O1795, O1796, O1797, O1798, O1799, M6531, M6532, M6533, O1690, O1730, 1740, O1750, O1760, O1770, O1781, O1782, O1783, O1810, O1826
End-stage of chronic kidney disease/ dialysis/ kidney transplant	N185, T824, Y602, Y612, Y622, Y841, Z49, Z992, E1022, E1122, E1222, E1322, E1422, Z940
Venous thromboembolism	I636, I676, I801, I802, I803, I808, I809, I81, I822, I823, I829, I26
Thyrotoxicosis	E05
Pericarditis	I30, I31, I32
Hypertrophic	I422

NIS Protocol <X9001134>
Statistical Analysis Plan
<Version 3.0> <03 May 2018>

Condition	KCD Code or Korean Procedure Codes
cardiomyopathy	

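### Sub-datasets 7-9 compare new NOAC users with an aspirin arm that has no washout, so time zero differs between the arms and no planned analysis aligns it

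*SAP*

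**What the plan says.** SAP 3.1 (Cohorts, item 3) defines sub-datasets 7, 8 and 9 as apixaban, dabigatran and rivaroxaban, each against aspirin. The index rule is "The index date will be defined as date of the first prescription of NOAC or aspirin in patients with NVAF during the intake period", with intake running from 1 July 2015 to 30 November 2016.

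Eligibility differs by arm:

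- **NOAC arm:** a one-year look-back "will be used and must indicate no OAC use during this period".
- **Aspirin arm:** the SAP describes it as "aspirin (no restrictions of antiplatelet or OAC use in the pre-index period". Protocol 8.2.2, item 7, agrees: "aspirin user is allowed to have OACs or antiplatelets in the pre-index period".

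SAP Appendix 2, Table 12, begins its antiplatelet list with "Aspirin, Clopidogrel, Prasugrel, Ticlopidine, Cilostazol". Aspirin is thus an antiplatelet, and allowing prior antiplatelets allows prior aspirin. The population statement in SAP 2.1 draws the same distinction: patients "who newly initiated NOACs, warfarin, or used aspirin between July 1, 2015 and November 30, 2016".

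Follow-up is on treatment: "Each patient was followed until discontinuation or switching of index treatment, outcome occurrence, or study ends (November 30, 2016". Confounding is handled by propensity scores. For the matched analysis, "1:1 matching without replacement will be performed", and covariate adjustment and IPTW are also planned. The only sensitivity analysis named (SAP 5.1; Protocol 8.7) is IPTW from a multinomial propensity model.

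**The concern.** A NOAC patient enters at a treatment decision after a year without any OAC. An aspirin patient may enter at a repeat prescription that is the index only because it is the first after an administrative date. In one arm, time since index is time since starting. In the other it is a mixture of time since starting and time since an arbitrary point in established use. Patients still taking aspirin at that point have neither died, stopped nor switched in the meantime.

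If the risk of bleeding or stroke is higher just after a start, the NOAC arm carries that period in full and the aspirin arm only in part. The hazard ratio then mixes the drug contrast with a contrast of treatment age. Primary objectives 2 and 3 both include the aspirin comparison, so the effectiveness and safety results are both exposed. Sub-datasets 1-6 do not share the problem, because both of their arms must be OAC-naive for a year.

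**Working it through.** **1. The plan's own figure.** There is none for the aspirin arm. The only planning number is about 150,000 patients for all treatments together (Protocol 8.5). It matches the 2015 count of 148,130 to within 1.2% ((150,000 − 148,130)/150,000). It says nothing about how many aspirin patients are continuing users.

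**2. Do the planned methods align time zero?**

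- *Baseline antiplatelet flag (SAP 4.4, Table 12).* It pools aspirin with eight other drugs and carries no duration. It does not separate a recent start from long use.
- *Listed propensity covariates (SAP 4.4, 5.1).* Neither time since first aspirin nor index calendar date is among them. The list is open, so both are unspecified rather than ruled out.
- *Multinomial IPTW.* It changes the weights and keeps the same cohort and index dates.
- *Proportional-hazards checks (SAP 5.1).* They run on time since index. They might show a ratio that falls over time, but would attribute it to treatment.
- *Limitations (Protocol 8.9).* The issue is not mentioned.

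**3. Possible share of continuing users.** Assume a constant rate *I* of aspirin starts per month and a mean duration of use of *D* months, with all users otherwise eligible. The pool already on aspirin when intake opens is *I·D*. New starters over the 17-month window number *I*·17. The continuing share is *D*/(*D* + 17).

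| Assumed *D* (months) | 6 | 12 | 17 | 24 | 36 | 60 |
|---|---|---|---|---|---|---|
| Continuing share | 26% | 41% | 50% | 59% | 68% | 78% |

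Continuing users are a majority only if *D* exceeds 17 months.

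**4. Size of the distortion when the true hazard ratio is 1.** All inputs are assumed:

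- baseline hazard of 3% per year in both arms, multiplied by *k* for the first 3 months after a start;
- continuing users at the baseline hazard throughout;
- continuing users entering evenly over the first 3 months of intake, and new users over all 17;
- exponential discontinuation with a mean of 24 months, and administrative end at month 17;
- 300,000 patients per arm, and a Cox model with treatment only.

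For a continuing share *s*, the hazard ratio at index follows directly as *k*/(*s* + (1 − *s*)*k*). With *k* = 2 this is 2/(0.4 + 1.2) = 1.25 at *s* = 0.4, 2/(0.6 + 0.8) = 1.43 at *s* = 0.6, and 2/(0.8 + 0.4) = 1.67 at *s* = 0.8. After 3 months the hazards in the two arms are equal. The Cox estimate averages the two periods:

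| *k* | *s* = 0 | *s* = 40% | *s* = 60% | *s* = 80% |
|---|---|---|---|---|
| 1 | 1.01 | 1.02 | 1.02 | 1.02 |
| 1.5 | 1.02 | 1.09 | 1.12 | 1.15 |
| 2 | 1.01 | 1.14 | 1.20 | 1.27 |
| 3 | 1.02 | 1.23 | 1.36 | 1.50 |

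The simulation standard error of the log hazard ratio is about 0.02, so 1.01 and 1.02 are close to the null. With no early excess (*k* = 1) there is no bias. With new aspirin users only (*s* = 0) there is none at any *k* shown.

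**The case against.** **The choice is deliberate and disclosed.** The SAP says openly that aspirin patients merely used the drug and that prior use is unrestricted. That stands as evidence of intent. It gives no reason for the choice, and disclosing an eligibility rule does not align time zero.

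**The aspirin arm is not shown to be mainly continuing users.** A reader might infer that it consists largely of them. No passage supports this, and the range above depends wholly on an assumed duration.

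**The direction is not fixed.** A reader might conclude that NOACs must look worse. That needs a raised early hazard, which no document supplies. The aspirin arm also admits patients who recently stopped an OAC, and they could push the ratio the other way. Nor are continuing users event-free survivors, because prior stroke or bleeding is not an exclusion.

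**Stronger claims about overlap rest on one reading.** Intake lasts 519 days. For index dates from 1 July 2016 (153 days, 29%) the one-year look-back lies wholly inside it. One might infer that no NOAC patient indexed then can have prior aspirin, that all continuing aspirin users enter in the first weeks, and that weights must become extreme. But the index rule refers to patients with NVAF, and the diagnosis may fall on the index date. An aspirin fill before an AF diagnosis therefore need not set the index. The planned covariate is any antiplatelet, so NOAC starters can carry the flag without aspirin. SAP 5.1 also provides for checking, stabilising, trimming or truncating weights. These inferences do not stand. What remains is that the SAP does not plainly say where a patient belongs who fills aspirin in the window and later starts a NOAC.

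**Matching may remove part of the problem.** If the antiplatelet flag enters the propensity model and overlap is poor, 1:1 matching would drop many continuing users. That is fair for the matched estimate. It depends on a covariate list not yet fixed, and covariate adjustment and untrimmed IPTW would keep those patients.

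**Conclusion.** The concern holds in limited form. Sub-datasets 7-9 set NOAC patients with a one-year OAC washout against aspirin patients with none, and nothing in the plan aligns time since initiation. That much follows from the text alone.

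The size cannot be fixed from the documents. With 40-80% continuing users, a true hazard ratio of 1 would appear as about 1.14-1.27 if hazard doubled for 3 months after a start, and as 1.23-1.50 if it tripled. It would be unchanged if there were no early excess. These figures illustrate the mechanism and are not predictions for this study. The net direction is uncertain once recent OAC stoppers are counted. The point merits a change to the SAP because the remedy is cheap, not because a particular bias has been shown.

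**What to change.** In SAP 3.1 and 5.1:

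1. Pre-specify for sub-datasets 7-9 an analysis limited to aspirin patients with no aspirin fill and no OAC fill from one year before to the day before the index date. Report it beside the unrestricted result.
2. Include index calendar quarter in the propensity model for these sub-datasets.
3. Report the share of the aspirin arm that had an aspirin fill in the look-back year.
4. Label the unrestricted contrast *new NOAC users versus current aspirin users*, and add the issue to the limitations in Protocol 8.9.
5. State which arm a patient joins who fills aspirin in the intake window before starting a NOAC.

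The cost is SAP wording and one further analysis per sub-dataset. Claims back to January 2007 are already requested (Protocol 8.6). The restricted analysis will have a smaller aspirin arm and wider intervals. Its washout is imperfect, because over-the-counter aspirin is not captured (Protocol 8.9.5) and some apparent new users will have taken aspirin before.
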